4.5 STUDY DURATION

The EVRA study will take 70 months to complete. The revised study timetable is summarised in Figure 4.

[figure not shown]

Figure 4. EVRA Study timeline

5. DETAILS OF INTERVENTIONS

5.1 VARIATIONS IN ENDOVENOUS INTERVENTIONS

A wide range of endovenous treatment modalities are now available and in widespread use for the ablation of superficial venous reflux. These include:

- Endovenous thermal ablation using laser or radiofrequency
- Ultrasound guided foam sclerotherapy (UGFS)
- Other endovenous interventions such as mechanochemical ablation, steam ablation and glue
- Any combination of the above treatments

In addition to the different modalities in use, the treatment strategy may also vary between institutions and between individual clinicians within the same department. Variations may occur in:

- Site of vein cannulation (and therefore the length of vein ablated)
- Location of treatment ('office' or clinic based versus operating theatre)
- Treatment strategy for sub-ulcer venous plexus (to ablate or not)
- The treatment of visible varicose veins (no treatment, UGFS or surgical avulsion) and the timing of any intervention

5.2 STANDARDISATION OF INTERVENTIONS IN EVRA STUDY

With the lack of consensus on a single, optimal endovenous treatment strategy for superficial reflux in patients with leg ulceration, perfect standardisation of interventions will be impossible. All endovenous interventions should be performed as deemed to be 'optimal' by the treating clinician for each individual patient, with the following stipulations:

1. The endovenous strategy must include ablation of the main truncal venous reflux
2. Truncal venous reflux should be treated to the lowest point of incompetence, where possible
3. Significant (as deemed by the treating clinician) residual / recurrent superficial reflux on the 6 week duplex scan, should be ablated
4. Patients should continue with multilayer compression / stockings immediately after treatment

5.3 STANDARDISATION OF COMPRESSION

Patients will receive the standard compression used in the individual centres prior to ulcer healing following randomisation (this will include four layer bandaging, three layer bandaging, European short stretch, stockings). Post healing the patients will be given compression hosiery in line with local policy.

5.4 FURTHER TREATMENT FOR STANDARD CARE (COMPRESSION ALONE) ARM

Patients randomised to multilayer compression / stockings alone can be offered endovenous treatment of superficial reflux once healing has been confirmed or at 6 month post randomisation (see 4.3.1). Endovenous ablation should be performed as per standard practice in the treating centre and details of this will be recorded. Endovenous intervention may also be offered if there is clinical deterioration in the active leg ulcer and it is clinically felt that the patient may benefit from early intervention. This will be recorded on the electronic case report form.

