2. OBJECTIVES

2.1 PRIMARY OBJECTIVE

To determine the clinical and cost effectiveness of early endovenous treatment of superficial venous reflux in addition to standard care compared to standard care alone in patients with chronic venous ulceration.

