7.1 SAMPLE SIZE CALCULATION

The sample size calculation for this study was based on the primary outcome of ulcer healing. The ESCHAR trial was a similar randomised study, which published the final results in 2007 (see 1.1.3). A total of 500 patients with open or recently healed venous ulcers were randomised to standard therapy alone or standard therapy plus open surgery for superficial venous reflux. The study was powered and designed to evaluate differences in ulcer recurrence (rather than healing).

Consequently, the median time from randomization to treatment delivery was over 7 weeks. Nevertheless, the 24-week healing rate in patients randomised to standard treatment (compression alone) was approximately 60%. Two recent prospective studies evaluating the early treatment of superficial venous reflux suggested that the 24-week healing rate may be as high as 82%^{24 25}.

In order to calculate a sample size for this study, a benefit associated with early treatment is estimated at around 15%. Assuming the 24-week healing rate in the standard arm is 60%, to identify a difference in 24-week healing rates of 15% between the two groups (60% vs 75%) with 90% power and allowing for 10% dropout the study will therefore require 416 subjects (208 in each arm, 254 healed leg ulcers in total). To incorporate further allowances for protocol violations and unexpected dropouts, the target sample size will be 450 patients.

Assuming a 15% drop out rate for the study and that 90% of primary ulcers eventually heal, it is estimated that >340 of the recruited 450 patients will be eligible for inclusion in the ulcer recurrence analysis. With this number of participants, and allowing for the healing rates (of the index ulcer prior to entry into this analysis of ulcer recurrence) to differ by up to 20% between the two study arms, the study extension will have at least 80% power to detect a difference of 15% or more in ulcer recurrence rates between the two arms at the 5% significance level.

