
#### 4.5 Ulcer Free Time to 1 year and 24-week Ulcer Healing Rate

Table 7 summarises the ulcer free time to 1 year and 24-week ulcer healing rate between the two arms. In the case that a patient is dead, withdrawn or lost to follow-up before 1 year, ulcer free time will be calculated as the time from randomisation until last follow-up. Multiple linear regression will be used to assess the difference between the treatments arms, with centre as a random effect, before and after adjustment for age, ulcer size and ulcer chronicity (Table 8). Graphical methods will be used to assess whether the assumption of normality is met. If the assumption of normality is not met, and there is no suitable transformation, ulcer free time will be categorized (by quartiles) and the analysis will instead be performed using ordinal regression. Model fit will be assessed using residual plots and/or goodness-of-fit tests, as appropriate. The 24-week healing rate and associated 95% confidence interval will be obtained from the Kaplan-Meier analysis (4.3). The primary analysis will be based on study participants with at least 1 year of follow up only (as explained in 2.2). As a sensitivity analysis we will repeat the above regression model (adjusted for age, ulcer size and ulcer chronicity, and centre) using all the study participants, irrespective of length of follow up.

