#### **4.9 Derived Variables**

1. Deep vein reflux is defined as iliac, femoral, popliteal or crural deep vein reflux detected by Duplex scan.
2. Deep vein obstruction is defined as iliac, femoral, popliteal or crural deep vein outflow obstruction detected by Duplex scan.
3. Time to ulcer healing will be calculated as the difference between the final healing date and date of randomisation. Final healing date is collected in the InForm database and this variable is entered by trial manager after experts agree on the healing date. Patients will be censored at the time of last follow-up if they are dead, withdrawn or lost to follow-up before primary ulcer healing. The follow-up time is one year after randomisation and thus patients with unhealed primary ulcer at one year after randomisation will be also censored.
4. One-year ulcer free time will be calculated as total follow-up time in days (i.e. one year or time to the last follow-up if patients are dead, withdrawn or lost to follow before one year) deducting the total duration of ulcers, including primary ulcer and recurrences.
5. Ulcer chronicity will be calculated as the difference between the date of current ulcer appeared and the date of randomisation.

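### Unhealed controls may be ablated from 6 months, inside the one-year primary window, and the plan names no between-arm estimate at 24 weeks, the time point the trial was sized on

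*Protocol*

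**What the plan says.** **Treatment of controls.** Under Protocol 5.4, patients in the compression arm "can be offered endovenous treatment of superficial reflux once healing has been confirmed or at 6 month post randomisation". The same section also allows earlier ablation if the active ulcer deteriorates, with no time limit. Protocol 9.2 leaves the clinician free to depart from the allocated treatment at any stage.

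**Primary analysis.** SAP 4.4 fits one Cox model to time to healing, with centre as a random effect. SAP 4.9 runs the endpoint to one year: "patients with unhealed primary ulcer at one year after randomisation will be also censored". There is no split at 6 months. Proportional hazards are to be checked by plots and Grambsch-Therneau tests, but SAP 4.4 does not say what follows if they fail.

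**24 weeks.** Protocol 7.1 sizes the trial "to identify a difference in 24-week healing rates of 15% between the two groups (60% vs 75%) with 90% power". For that time point SAP 4.5 says only: "The 24-week healing rate and associated 95% confidence interval will be obtained from the Kaplan-Meier analysis (4.3"). Table 7 lists the rate by arm. SAP 2.5 says secondary outcomes will be tested, but no test, difference or ratio is named for this one. The regression in SAP 4.5 is for ulcer free time.

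**Comparator.** The objective in Protocol 2.1, repeated in SAP 1.1, is "early endovenous treatment of superficial venous reflux in addition to standard care compared to standard care alone". Protocol 4 and SAP 1.3 define the control arm as compression with deferred treatment of reflux.

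**Deviations.** Protocol 7.6 and SAP 2.7 list any ablation of a control before verified healing as a protocol deviation, with no exception at 6 months. SAP 5 excludes patients with violations from the per-protocol analysis.

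**The concern.** Ablation after healing cannot affect time to first healing. The 6-month route is different: it applies to controls whose ulcers are still open, and after month 6 they are the only controls at risk. If they are ablated and it helps, the later part of the year compares early with late ablation, whereas the earlier part compares early ablation with compression while ablation is mostly withheld. One hazard ratio averages the two, and its size then depends on how many controls the sites choose to ablate at 6 months.

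At stake is what the headline estimate means. Someone who wants the gain over compression during the first months cannot read it from a one-year average that depends on uptake. The same holds for the decision model in Protocol 7.5, which needs relative risks against usual care and names bandaging only as a possible comparator. The period before the planned crossover would serve those uses better, and it is also the period behind the sample size, but no between-arm estimate is specified for it. If a 24-week contrast is chosen after the curves are seen, it can be challenged as selective.

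**Working it through.** **1. The plan's own figure.** Inputs from Protocol 7.1 and 7.2: 60% versus 75% healed at 24 weeks, 90% power, two-sided 5%, 10% dropout.

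- HR = ln(0.25)/ln(0.40) = 1.513.
- Freedman events = (1.960 + 1.282)² × [(1.513 + 1)/(1.513 − 1)]² = 253, against the stated "208 in each arm, 254 healed leg ulcers in total".
- Average proportion healed = (0.60 + 0.75)/2 = 0.675. Then 253/0.675 = 375, and 375/0.9 = 417, against 416.

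The sizing therefore reproduces as a log-rank calculation on events by 24 weeks.

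**2. Who is still at risk at 6 months.** Assume exponential healing at the design rates and take 6 months as week 26.

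- Controls unhealed: 0.40^(26/24) = 0.37, about 77 of 208 (83 of 225).
- Early arm unhealed: 0.25^(26/24) = 0.22.
- With no late ablation, unhealed at week 52: 0.137 and 0.050. Share of one-year events before week 26 = [1 − (0.371 + 0.223)/2] / [1 − (0.137 + 0.050)/2] = 0.703/0.906 = 78%. With all unhealed controls ablated it is 75%.

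So 22 to 25% of events fall after week 26.

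**3. One-year Cox hazard ratio by uptake.** Let λ0 = −ln(0.40)/24 and λ1 = −ln(0.25)/24 per week. A fraction f of controls unhealed at week 26 is ablated then and heals at λ1. After week 26, control survival is S0(t) = e^(−26λ0) × [(1 − f)e^(−λ0(t−26)) + f e^(−λ1(t−26))]. With event densities f0 and f1, the large-sample Cox estimate solves ∫{f1 − [e^β S1/(S0 + e^β S1)](f0 + f1)}dt = 0 over 0 to 52 weeks. Power = Φ(√D × ln HR/2 − 1.96), where D is the expected number of events among 374 evaluable patients (416 × 0.9) or 405 (450 × 0.9).

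| Uptake f | One-year HR | Fall in log HR | Power, 374 | Power, 405 |
|---|---|---|---|---|
| 0% | 1.51 | 0% | 0.97 | 0.98 |
| 25% | 1.48 | 6% | 0.95 | 0.96 |
| 50% | 1.44 | 12% | 0.92 | 0.94 |
| 75% | 1.41 | 18% | 0.89 | 0.91 |
| 100% | 1.37 | 24% | 0.83 | 0.86 |

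Power holds up because one year yields about 340 to 380 events against the 254 planned. Just after week 26 the hazard ratio is 1.513/[(1 − f) + 1.513f]: 1.20 at f = 50% and 1.00 at f = 100%. That is the built-in non-proportionality.

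**4. Sensitivity.** The documents give neither uptake nor the effect of late ablation. Two harsher assumptions:

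- Late ablation doubles the control hazard: HR 1.39 at 50% uptake (power 0.87 to 0.90) and 1.27 at 100% (0.61 to 0.65).
- The early-arm hazard falls back to the compression level after week 26, with ablated controls at 1.513 times it: HR 1.32 at 50% (0.73 to 0.76) and 1.25 at 100% (0.56 to 0.59).

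Nothing in the documents supports these two over the main case.

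**5. What a 24-week contrast would deliver.**

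- Cox model cut at 24 weeks: HR 1.513. Events 374 × 0.675 = 252, power 0.91; or 405 × 0.675 = 273, power 0.93.
- Difference of 15 points: SE = √[(0.60×0.40 + 0.75×0.25)/187] = 0.048, so the 95% CI is about ±9.4 points (±9.0 with 202 per arm). Power is 0.875 and 0.90 respectively.

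**6. The per-protocol analysis.** Protocol 5.4 permits ablation of an unhealed control at 6 months. Protocol 7.6 and SAP 2.7 record the same act as a deviation, and SAP 5 excludes violators. Read together, controls treated as 5.4 permits can be dropped. They are selectively slow healers, so removing them makes the control arm look better. This does not undo the dilution and may add to it.

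**The case against.** The strongest reply is that deferred ablation is the comparator. Protocol 4 and SAP 1.3 define it so. Protocol 1.2, 3.1 and 7.5 speak of early versus deferred or delayed treatment, and the title of SAP Figure 3 calls the control arm delayed. On that reading, ablation at 6 months is part of the control policy, and the one-year intention-to-treat hazard ratio estimates what was randomised. This stands. It moves the mismatch to the wording of the objective, which on its own reads as compression without ablation.

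Second, dilution is conditional. Ablation may be offered, not must be; about three quarters of events come before 6 months; and if late ablation helps, the bias is towards no effect, so a positive result is not inflated. This also stands, and it limits the point to effect size and interpretation.

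Third, the 24-week outcome is not ignored: it has a rate with CI per arm, SAP 2.5 promises a test, and a difference follows easily from two Kaplan-Meier estimates. True, but neither the contrast nor its method is named.

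Fourth, SAP 2.8 sends problems found in checking to a senior statistician, and a per-protocol analysis is planned. The first is a generic route, not a planned response to non-proportionality that can be foreseen from Protocol 5.4. The second is no substitute, for the reason in step 6.

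**Conclusion.** The point holds as one of interpretation and an incomplete specification. A planned treatment change in unhealed controls at 6 months falls inside a one-year endpoint that is summarised by a single hazard ratio. If late ablation is used and works, that ratio moves towards 1 with uptake: from 1.51 to 1.44 at 50% and 1.37 at 100%, a fall of 12% and 24% in the log hazard ratio. This rests on exponential healing at the design rates and on ablated controls healing at the early-arm rate from week 26. The plan states no between-arm contrast at 24 weeks.

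Three stronger readings are tempting, and the documents do not support them:

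- That the one-year hazard ratio is invalid or misses the trial's question. It is a sound estimate of early versus deferred ablation.
- That the first 24 weeks are a crossover-free comparison of ablation with no ablation. Protocol 5.4 allows earlier ablation on deterioration and Protocol 9.2 allows departures at any stage, so a 24-week result is an intention-to-treat estimate before the planned crossover and no more.
- That the trial is underpowered. Power is about 0.83 to 0.98 under the main assumptions, and drops to about 0.56 to 0.65 only with full uptake in the harsher scenarios.

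**What to change.** Keep the one-year intention-to-treat analysis as primary. In SAP 4.4 and 4.5 and Tables 6 and 7, pre-specify:

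- the between-arm difference in 24-week Kaplan-Meier healing, with 95% CI;
- the same Cox model with follow-up cut at 24 weeks, or period-specific hazard ratios before and after 6 months;
- the number of standard-arm patients ablated before healing, split at 6 months.

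Label the 24-week results as intention-to-treat estimates before the planned 6-month crossover, not as ablation versus no ablation. State that the one-year hazard ratio is early versus deferred ablation, and align the objective in Protocol 2.1 and SAP 1.1 with that. Protocol 5.4 must be reconciled with the deviation lists in Protocol 7.6 and SAP 2.7, so that the per-protocol analysis does not remove controls treated as the protocol permits. Which clinical rule should stand is not a statistical question and is left open here.

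The cost is a few lines of SAP text and some table rows, with no new data. The 24-week model has about a quarter fewer events (252 against 339 to 349 with 374 evaluable), so the CI for its log hazard ratio is about 16 to 18% wider: √(339/252) = 1.16 and √(349/252) = 1.18.

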6. ASSESSMENT AND FOLLOW-UP

6.1 PATIENT IDENTIFICATION

Patients will be referred to secondary care for evaluation of the management of their leg ulcer as part of the standard pathway of care.

6.2 REFERRAL VISIT

At the initial visit the patient will be evaluated by clinical assessment and colour duplex examination, which is part of the normal investigation of a patient with leg ulceration. Dependant on the results of these tests, the patient will be asked if they would consider taking part in the trial and approached for consent. The patient will be given a minimum of 24 hours to consider the trial and if willing to participate will return to the leg ulcer clinic to give consent and undergo a baseline visit.

6.3 BASELINE VISIT

Patients will undergo detailed clinical assessment by the research nurse as part of the baseline evaluation (see *Appendix 1*). Recorded assessments will include:

- Demographic details (age, sex, ethnicity)
- Pregnancy test for woman of child bearing potential
- General clinical details (body mass index, ankle brachial pressure index – performed within previous 4 weeks, comorbidities, medication history)
- Ulcer details (duration, progression, previous ulcer history, size of current ulcer – using photography and planimetry)
- Details of venous disease (previous deep vein thrombosis, previous venous interventions, pattern of venous reflux on duplex)

Additional assessments will include:

- Assessment of Clinical, Etiologic, Anatomic, Pathophysiological (CEAP) score
- Assessment of venous clinical severity score (VCSS)
- Disease specific (Aberdeen varicose vein questionnaire – AVVQ) and generic (EuroQoL 5D – EQ5D & short form (SF) 36) quality of life assessments

At this visit, eligible and consenting patients will be randomised into the trial.

6.4 FOLLOW-UP ASSESSMENTS

Randomised patients will undergo routine leg ulcer care in community or hospital (or both) settings, in accordance with the local standard. This will equate to wound reviews and dressing changes ranging between once and 4 times per week (depending on the ulcer). The exact nature of dressings and date of dressing change will be documented by the completion of patient diaries. This will allow an accurate record of the dressing types used and will be collected and verified by the research nurse.

In addition, the following assessments will be conducted:

6.4.1 6-week clinic visit

- Clinical assessment
- In the compression plus early venous reflux ablation group, venous duplex scanning will be performed at 6 weeks post-randomization to verify anatomical treatment success. Depending on the results of the scan, the decision to perform further superficial venous interventions will be left to the discretion of the responsible clinical staff. Irrespective of the number and timing of venous interventions, all analyses will be performed on intention to treat.
- Wound tracing and photo
- Assessments of disease specific and generic quality of life (AVVQ, EQ5D & SF36) by means of self-completed questionnaire

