4. Health Economic Assessment: A within-RCT cost effectiveness analysis will be carried out based on the data collected in the trial. Resource use items in hospital and community care related to the treatment of venous ulceration or complications will be recorded for each patient at each follow-up. Resource use will be multiplied by UK unit costs obtained from published literature, HRG costs, and manufacturers' list prices to calculate overall costs. A standard tariff will be applied for each bandage change. Utilities (QALYs) will be calculated from the EQ-5D questionnaire administered to patients at baseline, 6 weeks, 6 months, 12 months and at one time point between October 2018 and March 2019. The extent of missing data will be assessed and appropriate methods to handle missing data will be applied if necessary. The incremental cost-effectiveness ratio will be calculated and compared to current UK decision making thresholds. Discounting will be applied at the standard rate. Sensitivity analysis will be carried out to test the robustness of results to alternative assumptions (for example, about missing data, or using per-protocol estimates of treatment effect) or alternative data (for example, about unit costs). Probabilistic sensitivity analysis will be carried out using bootstrapping. A decision model will also be constructed to take account of

outcomes (such as recurrence or healing) that might occur beyond time horizon of the RCT, or to take account of other relevant comparators in this patient group.

5. Other Markers of Clinical Success: The Venous Clinical Severity Score (VCSS) will be assessed at 6 weeks. In addition, the incidence of complications related to the endovenous intervention as well as the presence of residual / recurrent varicose veins will also be assessed at 6 weeks in the early arm.

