6.5 URGENT VERIFICATION VISIT

- A member of the local research team will perform the four verification visits to confirm healing. Photographs will be taken and send to the Trials Unit for independent verification. In order to minimise inconvenience to the participants, once core labs confirms healing it is not necessary for the research team to perform further verification visits. Please note all four photos should be taken unless the trial manager confirms otherwise.

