8. ADVERSE EVENTS

8.1 REPORTING PROCEDURES

During the first 12 months all serious adverse events and all intervention-related adverse events should be reported. Any serious adverse events reported at the October 2018 to March 2019 follow-up time point should be reviewed by the Principal Investigator to assess whether they are related to the treatment pathway and only related events should be reported to the sponsor via INFORM. Depending on the nature of the event the reporting procedures below should be followed. Any questions concerning adverse event reporting should be directed to the Chief Investigator in the first instance.

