8.2 RELATED ADVERSE EVENTS

Patients randomised to early venous intervention have the potential risks of treatment. Competent, experienced medical staff will perform all procedures and every effort will be made to prevent adverse effects. The adverse events listed below are expected to be related to the endovenous interventions used in the trial and should be reported. **Please note this is not an exhaustive list, if you suspect an event is related to treatment please contact the Trials Unit.**

Systemic

- **allergic reaction req. local / no treatment**
- **migraine**
- **visual disturbance**
- **fainting**
- **Cough / chest tightness**
- **Systemic infection**
- **PE**
- **TIA**
- **Stroke**

Local

- **Bleeding requiring intervention**
- **Blistering of skin**
- **Pressure damage**
- **Nerve damage**
- **DVT**
- **Hematoma**
- **Patient reported paresthesia**
- **Pigmentation of skin**
- **Superficial thrombophlebitis**
- **New ulcer**
- **Deterioration of ulcer**
- **Wound infection**

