Appendix 1: Summary of assessments and follow-up visits

Time point	Estimated duration (mins)	Clinical evaluation*	Telephone follow-up**	Wound review/photo /tracing***	Collection of further endovenous intervention / duplex report	Venous duplex	Randomisation	Consent	Health Questionnaires (EQ-5D, SF-36, AVVQ)
Screening Visit	45	X				X		X ^a	
Baseline Visit	60-90	X		X***			X	X ^b	X
1 month	30		X						
6 weeks	60-90	X		X ^{?****}		X ^c			X
2 months	30		X	X [?]					
3 months	30		X	X [?]					
4 months	30		X	X [?]					
5 months	30		X	X [?]					
6 months	30		X	X [?]					X
7 months	30		X	X [?]					
8 months	30		X	X [?]					
9 months	30		X	X [?]					
10 months	30		X	X [?]					
11 months	30		X	X [?]					
12 months	30		X	X [?]					X
Extension follow-up Oct18 to Mar 19	240	X ^d	X		X			X ^e	X

*. Demographic details (age, sex, ethnicity), Pregnancy test for woman of child bearing potential. General clinical details (body mass index, ankle brachial pressure index – performed within previous 4 weeks, comorbidities, medication history). Ulcer details (duration, progression, previous ulcer history, size of current ulcer – using photography and planimetry). Details of venous disease (previous deep vein thrombosis, previous venous interventions, pattern of venous reflux on duplex)

. Ulcer healing assessment, compression type, AE assessment, Concomitant medications, health resource use. *tracing only performed at baseline & 6 weeks

a. Approached b Taken c. Only for those who have early endovenous treatment d. review of clinical notes only e. patients will not be reconsented as already consented for longer term follow-up at outset but will be asked if they wish to continue

?dependant on whether the ulcer has healed photo will be taken at verification visit and taken weekly for 4 weeks, unless otherwise confirmed by the trial manager. Once the ulcer has healed the patient will still be followed up with monthly phone calls.

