#### ***Secondary Outcomes***

- Ulcer Healing Rate: 24-week healing rate will be reported in addition to time to ulcer healing.
- Ulcer reoccurrence / Ulcer Free Time: Will be calculated up to 1 year for each study arm.
- Quality Of Life (QoL): Disease specific (AVVQ) and generic (EQ5D & SF36) quality of life assessments will be compared at 6 weeks post randomisation, 6 months and 12 months.
- Health Economic Assessment
- Other Markers of Clinical Success: The Venous Clinical Severity Score (VCSS) and will be assessed at 6 weeks. In addition, the incidence of complications related to the endovenous intervention as well as the presence of residual / recurrent varicose veins will also be assessed at 6 weeks.

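### Deferred-ablation complications that need a scan or examination to be seen are liable to be under-counted in SAP Table 11, because only the early arm has a scheduled check after ablation

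*Protocol*

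**What the plan says.** **Early arm.** Ablation is due within 2 weeks of randomisation (Protocol 4). Section 6.4.1 then states: "In the compression plus early venous reflux ablation group, venous duplex scanning will be performed at 6 weeks post-randomization to verify anatomical treatment success". Note c to the duplex column of Appendix 1 reads "Only for those who have early endovenous treatment". Under 4.3.2 item 5, intervention complications and residual or recurrent varicose veins "will also be assessed at 6 weeks in the early arm".

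**Compression arm.** Under 5.4, these patients "can be offered endovenous treatment of superficial reflux once healing has been confirmed or at 6 month post randomisation", or earlier if the ulcer deteriorates. The procedure follows the centre's usual practice and its details are recorded. No scan or visit is tied to it. The arm does attend the 6-week clinic visit for a clinical assessment.

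**Common to both arms.** Staff telephone monthly for 12 months and consult community notes or nurses (6.4.2, 8.4). Section 8.1 sets one duty: "During the first 12 months all serious adverse events and all intervention-related adverse events should be reported". Section 8.2 adds "The adverse events listed below are expected to be related to the endovenous interventions used in the trial and should be reported"; its list includes DVT, hematoma, nerve damage and skin pigmentation.

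**Reporting.** Safety is presented by arm on an intention-to-treat basis (7.2). SAP 4.8 and Table 11 give total, systemic and local adverse events by arm, with a row for the number of surgical procedures. They have no split by how an event was found and no caveat on unequal search. SAP 1.4 repeats the 6-week outcome as "recurrent varicose veins will also be assessed at 6 weeks", without the protocol's limit to the early arm.

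**The concern.** The reporting duty is equal but the search is not. An early ablation is followed by a scheduled scan and a complication assessment. A deferred ablation is followed only by what both arms get (calls, notes, nurses) and whatever the centre does locally. For an event that the patient notices, this makes little difference. For an event that a scan or an examination shows, it can.

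The plan does make this comparison. If the true complication risk per ablation were the same in both arms, Table 11 could still show more local events or DVTs with early ablation. A reader could not separate the effect of timing from the effect of looking. The expected bias runs against early ablation, the strategy under test.

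**Working it through.** The plan states no figure on this point, so there is none to reproduce. The check has three parts.

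**1. When the early-arm check falls.** Ablation is at week 0 to 2 and the visit is at week 6. The check therefore falls 6 − 2 = 4 to 6 − 0 = 6 weeks after the procedure.

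**2. How often the 6-week visit follows a deferred ablation.** Inputs from Protocol 7.1: 60% healed at 24 weeks in the standard arm and 90% of primary ulcers healing eventually. Section 1.1 gives 60% to 65% for published trials. Assumptions: exponential healing towards the 90% ceiling, and ablation W weeks after healing, done by week 52.

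- F(t) = 0.90 × (1 − exp(−rt)). Setting F(24) = 0.60 gives r = ln(3)/24 = 0.0458 per week.
- Share ablated before the 6-week visit = F(6 − W)/F(52 − W).
- W = 0: 0.216/0.817 = 0.26.
- W = 4: 0.079/0.800 = 0.10.
- W = 6 or more: 0.
- 65% healed at 24 weeks, W = 0: 0.247/0.844 = 0.29.

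The range is 0% to 29% of post-healing deferred ablations. Ablation of an unhealed ulcer at 6 months always comes after the visit. Ablation for deterioration may come before it, and the documents do not say how often. Even where the visit does follow a deferred ablation, the protocol schedules no scan and assigns the complication assessment to the early arm.

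**3. What unequal detection could do (illustration only).** The documents give no complication rates, no detection probabilities and no uptake of deferred ablation. Assume:

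- 225 patients per arm (half of 450)
- 95% of the early arm and 70% of the compression arm ablated within the year
- the same true rate in both arms, 10% per ablation, of events that need a scan or examination
- full detection in the early arm, and a share d detected after deferred ablation

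Early arm, seen: 225 × 0.95 × 0.10 = 21.4. Compression arm, true: 225 × 0.70 × 0.10 = 15.8.

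| d | Compression arm, seen | Compression arm, missed | Apparent early:deferred ratio per ablation (1/d) |
|---|---|---|---|
| 0.25 | 3.9 | 11.8 | 4.0 |
| 0.50 | 7.9 | 7.9 | 2.0 |
| 0.75 | 11.8 | 3.9 | 1.33 |
| 1.00 | 15.8 | 0 | 1.0 |

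These ratios apply only to events of that kind. Once symptomatic events at rate s per ablation, found equally in both arms, are added to scan- or examination-dependent events at rate q, the ratio is (s + q)/(s + dq):

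- s = 0.20, q = 0.01, d = 0.75: 0.21/0.2075 = 1.01.
- s = 0.05, q = 0.10, d = 0.25: 0.15/0.075 = 2.0.

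The effect could thus be trivial or large. The procedure count in Table 11 corrects for fewer ablations in the compression arm. It does not correct for d.

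**The case against.** Several points stand against a stronger reading.

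- **That deferred complications are under-counted, as a fact.** A reader might infer this, but the documents support only an expected direction. Local practice may include a scan or review after deferred ablation, and anything found there is reportable.
- **That only the monthly call is left after deferred ablation.** This is wrong. Notes and community nurses are also consulted monthly (6.4.2), and wound reviews one to four times a week continue for patients ablated while still unhealed. A patient may also report a visible hematoma or pigmentation by telephone.
- **That the scan is a search for complications.** Its stated purpose is anatomical success, so complications would be incidental findings. The separate complication assessment in 4.3.2 is the clearer asymmetry.
- **That the healing verification visits widen the gap.** Section 6.5 says "A member of the local research team will perform the four verification visits to confirm healing". It mentions no adverse-event check, so nothing is built on those visits here.
- **That any early-arm excess is a detection effect.** Under 5.2 item 3, significant residual reflux on the 6-week scan should be ablated. Complications of those further procedures are real.
- **That the SAP plans a two-arm complication comparison at 6 weeks.** SAP 1.4 could be read so, but no SAP section or table makes that comparison. The wording only needs aligning with the protocol.

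It is also fair that SAP 4.8 is descriptive, with no test or effect estimate, and that safety is not a listed objective. That limits the weight of the point. The by-arm table will still be read as a comparison, and nothing in it warns that the search differed.

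**Conclusion.** The point holds as a limited one about ascertainment. Scheduled post-ablation checking exists in the early arm only, and the resulting counts are shown by arm without adjustment or caveat. Complications of deferred ablation that need a scan or examination to be seen are therefore liable to be under-counted relative to early ablation. The 12-month window is inferred from Protocol 8.1 and the SAP's one-year follow-up, since Table 11 carries no time label.

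The 0% to 29% figure rests on the exponential healing curve and on the assumed wait, and it leaves out ablation for deterioration. The event counts and ratios are scenarios, not estimates. Symptomatic and serious events are little affected, and time to healing is not affected. This is worth considering as a cheap improvement to the safety table; it is not a flaw in the trial's main conclusion.

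**What to change.** 1. In SAP 4.8 and Table 11, keep the row for all events. Add a by-arm sensitivity row, overall and for DVT, that excludes intervention-related events first found at the protocol 6-week scan or complication assessment. Show both beside the number of procedures.
2. State the limits of the second row. It may remove events that the patient would have reported at the next call. Events from re-ablation prompted by the scan (Protocol 5.2 item 3) are real early-arm events and stay in both rows. Do not claim that the two rows bracket the truth.
3. Footnote Table 11 to say that the scheduled scan and 6-week complication assessment applied to the early arm only. In SAP 1.4, add the protocol's restriction of that assessment to the early arm.

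The cost is one extra row block, one footnote and a small check of notes for early-arm events dated at the 6-week visit. That classification would be unblinded. No new visit is needed and the primary analysis does not change.
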